### I 3.3 Guidance for Management of Savolitinib Specific Toxicities

**Hypersensitivity:** Hypersensitivity, which may manifest as a constellation of symptoms such as but not limited to pyrexia, allergic skin reaction, increased liver enzymes, cytopenia, or myalgia and/or arthralgia has been reported after savolitinib dosing. These reactions have occurred within days to weeks after the first dose but the majority of reactions have occurred in the first six weeks of therapy. Patients with suspected savolitinib-related hypersensitivity (excluding confirmed infective aetiology), may be managed with corticosteroids, antihistamines and antipyretics (doses and duration of treatment according to local practice at the discretion of the investigator). Dose interruption with savolitinib should be avoided, if possible. Some patients who experienced the initial hypersensitivity reaction also reported severe acute hypersensitivity reactions, including anaphylaxis, upon restarting savolitinib treatment following a short period of interruption.

**Restarting savolitinib:** acute hypersensitivity including anaphylaxis has been observed in a number of patients mostly upon savolitinib restart. If interruption of savolitinib occurs in the first 6 weeks of savolitinib due to savolitinib-related general toxicities, or specific hypersensitivity toxicities occur at any time, dosing with savolitinib may be resumed but at a reduced dose, only after consultation with and approval from the study physician and with the following management:

- Treatment:
  - Pre-treatment with systemic corticosteroids must be started at least 24 hours before the restart of savolitinib;
  - Pre-treatment with antipyretics and antihistamines on the day of restart of savolitinib;
  - Doses of antihistamines, corticosteroids and antipyretics should be according to labelling instructions/product information.
  - These medications must be continued daily until discontinuation of savolitinib, but doses of steroids may subsequently be tapered according to local practice
- Intense medical monitoring (restart at the institution);
  - The restart of savolitinib must be performed in the hospital/institution where the clinical study is carried out with medical equipment readily available for resuscitation and management of anaphylaxis
  - Vital status recording (BP, temperature, respiratory rate, heart rate, etc) before administration of savolitinib, every 15 minutes after savolitinib dosing for the first hour, every 30 minutes for the next hour and hourly for a total of at least 4 hours and
  - Patient must be observed in the clinic for 24 hours before discharge.

- Should the symptoms recur, or an acute anaphylactic reaction occurs, immediate intervention must be instituted for appropriate management of event and savolitinib must be permanently discontinued.

Any recommendations regarding hypersensitivity management or pre-treatment should be used as guidelines only. Final decisions concerning management of individual patients reside with the investigator or the treating physician.

## Appendix J Guidance Regarding Potential Interactions with Concomitant Medications

The use of any natural/herbal products or other “folk remedies” should be discouraged, but use of these products, as well as use of all vitamins, nutritional supplements and all other concomitant medications must be recorded in the eCRF.

### J 1 Drugs Inducing CYP3A4 Metabolism that AstraZeneca Strongly Recommend are not Combined with Osimertinib or Savolitinib

Osimertinib and savolitinib are metabolised by CYP3A4 and CYP3A5 enzymes.

A drug-drug interaction study of osimertinib evaluated in patients showed that there is potential for osimertinib being a victim when co-administered with strong inducers of CYP3A4 (osimertinib concentrations are decreased when co-dosed with rifampicin).

The following potent inducers of CYP3A4 must not be used during this study for any patient receiving osimertinib or savolitinib.

**Table J1 Drugs Inducing CYP3A4**

Contraindicated drugs	Withdrawal period prior to osimertinib or savolitinib start
Avasimibe, carbamazepine, mitotane, phenobarbital (phenobarbitone), phenytoin, rifampicin, rifabutin, rifapentin St John’s Wort	3 weeks
Enzalutamide	5 weeks

CYP = Cytochrome P450.

This list is not intended to be exhaustive, and a similar restriction will apply to other agents that are known to strongly modulate CYP3A4 activity. Appropriate medical judgment is required. Please contact AstraZeneca with any queries you have on this issue.

### J 2 Drugs Inhibiting CYP1A2 Metabolism that AstraZeneca Strongly Recommend are not Combined with Savolitinib

**Table J2 Drugs Inhibiting CYP1A2**

Contraindicated drugs	Withdrawal period prior to savolitinib start
Ciprofloxacin, Enoxacin, Clinafloxacin Fluvoxamine	2 weeks

CYP = Cytochrome P450.

This list is not intended to be exhaustive, and a similar restriction will apply to other agents

that are known to strongly inhibit CYP1A2 activity. Appropriate medical judgment is required. Please contact AstraZeneca with any queries you have on this issue.

Savolitinib is a weak inhibitor of Organic Anion Transporter Protein B1 and B3, and BCRP. The use of statins should be avoided as far as possible and if considered necessary, the patients should be given the lowest available dose and closely monitored for the effects of increased statin exposure.

### **J 3 Medicines whose Exposures may be Affected by Osimertinib that AstraZeneca Considers may be Allowed with Caution**

Osimertinib may increase the concentrations of sensitive BCRP or P-gp substrate (concentrations of sensitive BCRP substrate, rosuvastatin or P-gp substrate, fexofenadine is increased).

**Table J3 Exposure, Pharmacological Action and Toxicity may be Increased or Decreased by Osimertinib**

Warning of possible interaction	Advice
Rosuvastatin Sulfasalazine Doxorubicin Daunorubicin Topotecan Aliskiren Dabigatran etixelate Digoxin	Drugs are permitted but caution should be exercised and patients monitored closely for possible drug interactions. Please refer to full prescribing information for all drugs prior to co-administration with osimertinib.

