#### 4.1.1 Randomised Study Design

Prior to CSP V3.0, approximately 56 patients were planned to be randomised in a ratio of 1:1 to receive treatment with CCI savolitinib CCI plus CCI osimertinib CCI or CCI savolitinib CCI plus placebo. At least half of the patients randomised into the study will be second-line patients who were treated with osimertinib as first-line therapy. Randomisation will be stratified according to the number of prior lines of therapy (ie, osimertinib monotherapy as first line or  $\geq$  second line [which includes patients who received osimertinib monotherapy before or after chemotherapy]).

Prospective testing of tumour specimens to determine MET amplification by central FISH using tumour specimens collected after progression on prior treatment with osimertinib should be performed at Pre-screening in advance of Screening for the main study. Patients determined to be MET amplified in Pre-screening will undergo screening during the 28 days prior to randomisation to confirm eligibility ([Sections 5.1](#) and [5.2](#)).

Provision of a FFPE tumour specimen is mandatory (refer to the Laboratory Manual for detailed specimen requirements). This will be used for prospective analysis of MET amplification by FISH.

Patients will continue to receive study medication CCI in 28-day cycles until objective PD by RECIST 1.1 is assessed, unacceptable toxicity occurs, consent is withdrawn or another discontinuation criteria is met ([Section 7](#)). At the time of investigator assessment per RECIST 1.1 of PD, the randomisation blind can be broken and patients who were initially randomised to the savolitinib plus placebo arm will be given the opportunity to cross-over (see [Sections 4.1.2](#) and [6.3](#)). Patients originally randomised to savolitinib plus osimertinib may continue to receive treatment with savolitinib plus osimertinib or osimertinib monotherapy (if savolitinib was stopped earlier) beyond RECIST 1.1 defined PD as long as they continue to receive clinical benefit, in the opinion of the investigator, and do not meet any of the

discontinuation criteria. No other anti-cancer agent is permitted in combination with osimertinib within this study. Patients can continue on savolitinib monotherapy (if randomised to the savolitinib plus placebo arm or if osimertinib was stopped earlier) until objective PD by RECIST 1.1 is assessed. Savolitinib monotherapy post-progression is not permitted.

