## **6.5 Concomitant Therapy**

Any medication or vaccine (including over-the-counter or prescription medicines, vitamins, and/or herbal supplements or other specific categories of interest) that the patient is receiving at the time of enrolment or receives during the study must be recorded along with:

- Reason for use
- Dates of administration including start and end dates
- Dosage information including dose and frequency

The Medical Monitor should be contacted if there are any questions regarding concomitant or prior therapy.

For patients continuing treatment with osimertinib during Screening, the date and time of administration of the last dose of osimertinib prior to Cycle 1 Day 1 (prior to PK sampling) should be recorded.

Medication other than that described in [Appendix J](#), which is considered necessary for the patient's safety and wellbeing, may be given at the discretion of the investigator and recorded in the appropriate sections of the eCRF.

Guidance on medicines to avoid, medications that require close monitoring, and washout periods is provided in [Appendix J](#) and a list of medicines to avoid is kept up to date at the following: <http://medicine.iupui.edu/clinpharm/ddis/main-table>.

The use of medications listed in [Table 6](#) is restricted, these medications are permitted with caution and careful monitoring of patients.

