#### **9.4.2.1 Analysis of Primary Endpoint**

Objective response rate by investigator assessment in accordance with RECIST 1.1 is the primary endpoint for this study.

The ORR is defined as the proportion of patients with an investigator-assessed response of CR or PR by RECIST 1.1.

Data obtained up until progression, or last evaluable assessment in the absence of progression, will be included in the assessment of ORR. Patients who discontinue treatment without progression, receive a subsequent anti-cancer therapy (note that for this analysis radiotherapy is not considered a subsequent anti-cancer therapy) and then respond will not be included as responders in the ORR.

The ORR will be analysed using a logistic regression model adjusting for the stratification used in the randomisation. The results of the analysis will be presented in terms of an odds ratio (an odds ratio greater than 1 will favour savolitinib in combination with osimertinib versus savolitinib in combination with placebo) together with its associated profile likelihood 95% CI and p-value (based on twice the change in log-likelihood resulting from the addition of a treatment factor to the model).

If there are not enough responses for a meaningful analysis using logistic regression then a CMH test will be presented.

Summaries will be produced that present the number and percentage of patients in each treatment group with a tumour response (CR/PR).

A sensitivity analysis of the ORR will be performed based on the BICR assessment of disease progression by RECIST 1.1. Further sensitivity analyses will be described in the SAP.

Summaries will be produced that present the number and percentage of patients in each treatment group with a tumour response (CR/PR). Summaries will also be produced for ORR per BICR.

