#### **9.4.3 Safety**

Safety and tolerability will be assessed in terms of AEs, SAEs, discontinuation rate due to AEs, deaths, laboratory data, vital signs, ECHO data, ECG data and ECOG performance status. All safety analyses will be performed on the SAS. Data will also be presented separately for patients who crossed over to savolitinib plus osimertinib upon investigator-assessed PD per RECIST 1.1 on savolitinib plus placebo. Safety data will be presented using descriptive statistics unless otherwise specified.

Adverse events will be coded using the most recent version of MedDRA that have been released for execution at AstraZeneca. Adverse events will be graded according to the National Cancer Institute CTCAE (Version 5.0).

The number of patients experiencing each AE will be summarised by the MedDRA system organ class, preferred term and treatment group. The number and percentage of patients with AEs in different categories (eg, causally related, CTCAE Grade  $\geq 3$  etc) will be summarised, and events in each category will be further summarised by MedDRA system organ class, preferred term and treatment group. If there are sufficient SAEs, they will be summarised separately. Further details will be provided in the SAP.

Adverse events occurring prior to the start of study intervention, treatment-emergent AEs and post-treatment emergent AEs will be presented separately. Adverse events occurring in the savolitinib in combination with placebo group will be split into 2 presentations based on whether they occurred before or after the crossover into the savolitinib in combination with osimertinib group.

Any AE occurring before the first dose of study intervention will be included in the data

listings but will not be included in the summary tables of AEs. Adverse event summary tables will include only treatment-emergent AEs. The following events are considered treatment emergent:

- Adverse events with an onset date on or after the first dose of randomised study intervention and within the safety follow-up period (28 days [ $\pm$  7 days] after last dose of all study intervention). Any events in this period that occur after a patient has received further therapy for cancer (following discontinuation of all study intervention) will be flagged in the data listings.
- Worsening of pre-existing events on or after the first dose of study intervention and within the safety follow-up period.

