### **J 4 Medicines whose Exposures may be Affected by Savolitinib that AstraZeneca Strongly Recommend are not Combined with Savolitinib**

Cytochrome P450 3A4 substrates which have a narrow therapeutic range must not be taken within 2 weeks of the first dose of savolitinib treatment (3 weeks for St John's Wort) and for 3 weeks after the last dose of savolitinib.

Patients are not permitted to receive warfarin when patients are treated with savolitinib. Low molecular weight heparin is allowed.

Any cytotoxic chemotherapy, investigational agents or other anti-cancer drugs for the treatment of advanced NSCLC from a previous treatment regimen or clinical study within 14 days of the first dose of savolitinib.

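### Table J3 permits three cytotoxic drugs with osimertinib although Sections 4.1.1 and 4.1.2 permit no other anti-cancer agent with it, and the ORR exclusion in 9.4.2.1 would not catch a response on concurrent chemotherapy

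*Supplement*

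**What the plan says.** **Concomitant drugs.** Section 6.5 states: "Guidance on medicines to avoid, medications that require close monitoring, and washout periods is provided in" Appendix J. Within it, J 3 covers medicines whose exposure osimertinib may alter and which the sponsor considers allowable with caution. Table J3 there includes "Doxorubicin Daunorubicin Topotecan", and its advice column reads "Drugs are permitted but caution should be exercised and patients monitored closely for possible drug interactions".

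**Design sections.** Section 4.1.1 says: "No other anti-cancer agent is permitted in combination with osimertinib within this study". Section 4.1.2 says the same for patients who cross over.

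**Primary endpoint.** Section 9.4.2.1 sets the data window: "Data obtained up until progression, or last evaluable assessment in the absence of progression, will be included in the assessment of ORR". Its only provision on other treatment begins "Patients who discontinue treatment without progression, receive a subsequent anti-cancer therapy" and goes on to say that those who then respond are not counted as responders. Radiotherapy is not treated as such a therapy.

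**Adverse events.** Section 9.4.3 flags in the listings, and leaves out of the summaries, events that occur after "further therapy for cancer (following discontinuation of all study intervention").

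**The concern.** A site that looks up topotecan or doxorubicin where Section 6.5 tells it to look finds the drug permitted with osimertinib. A site that reads the design section finds it barred. The two texts deal with the same situation, co-administration with osimertinib, and neither refers to the other.

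The statistical interest lies in the primary endpoint. The trial exists to separate the contributions of two drugs by comparing response rates. The ORR exclusion shows an intention not to credit study treatment with a response that another anti-cancer therapy may have produced. It does this only when study treatment was discontinued first. If a cytotoxic drug were added while study treatment continued, as Table J3 literally allows, a response before progression would count for the randomised arm.

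**Working it through.** **Step 1: is the conflict resolved anywhere?**

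| Place | What it contributes |
|---|---|
| Sections 4.1.1 and 4.1.2 | No other anti-cancer agent with osimertinib |
| Table J3 | Three cytotoxics permitted with osimertinib, with caution |
| Section 6.5 | Refers to Appendix J; states no general ban on anti-cancer drugs |
| Table 6 | No row on anti-cancer drugs |
| J 4 | Has an entry beginning "Any cytotoxic chemotherapy, investigational agents or other anti-cancer drugs for the treatment of advanced NSCLC from a previous treatment regimen or clinical study within"; its limit is a two-week window at the start of savolitinib, not the whole of treatment |

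No place settles it. In 4.1.1 the ban also follows text about treatment beyond progression. It is worded for the whole study, but a reader who confined it to that context would find no explicit on-treatment ban before progression.

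**Step 2: which concurrent use can reach the ORR?**

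- Cytotoxic started after progression: outside the ORR data window, so no effect on ORR.
- Cytotoxic started after study treatment was stopped without progression: caught by the existing exclusion.
- Cytotoxic started before progression while study treatment continues: inside the data window and not caught. This is the only gap.

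**Step 3: how much does one patient weigh?** The plan gives no figure for this. The stated plan is 56 patients, 28 per arm (Section 9.2). Version 3.0 says that number will not be reached and does not give the achieved size, so the smaller sizes below are assumptions. The shift in an arm's ORR from one added response is 1/n.

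| n per arm | 1/n |
|---|---|
| 28 (planned) | 3.6 points |
| 20 (assumed) | 5.0 points |
| 14 (assumed) | 7.1 points |
| 10 (assumed) | 10.0 points |

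**Step 4: could it change the test?** This illustration uses assumed counts of 12/28 on the combination and 3/28 on savolitinib plus placebo. With x and y responders, OR = x(n − y) / [(n − x)y]. Fisher's exact test stands in for the planned logistic regression.

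| Scenario | OR | Fisher p |
|---|---|---|
| No misattributed response | 12×25 / (16×3) = 6.25 | 0.014 |
| One added, placebo arm | 12×24 / (16×4) = 4.50 | 0.037 |
| Two added, placebo arm | 12×23 / (16×5) = 3.45 | 0.080 |
| One added, combination arm | 13×25 / (15×3) = 7.22 | 0.007 |
| Two added, combination arm | 14×25 / (14×3) = 8.33 | 0.003 |

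With these counts it takes two misattributed responses in the placebo arm to move the result across the two-sided 5% level. The table shows sensitivity only. It says nothing about how often this would happen.

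**The case against.** The best defence is that Table J3 is an interaction list. It concerns substrates of two transporters, its first column is headed as a warning, and it does not set out a treatment route. The design sections state the ban twice, and Section 7.1.2 places other therapy after permanent discontinuation, which is the sequence the ORR and AE rules assume. To exploit the gap, a site would have to add a cytotoxic to blinded study drug in a patient who has not progressed. Concomitant medication is recorded with dates, and decisions on evaluability are made before unblinding. The SAP is not among the documents, and Section 9.4.2.1 leaves further sensitivity analyses to it.

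Most of this stands as to frequency: such use is probably rare, and any case could be identified. It does not remove the literal contradiction, and the protocol's own ORR rule remains tied to discontinuation.

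A reader might infer more than the documents support:

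- *That OS and PFS are distorted.* Section 9.4.2.2 defines both regardless of other anti-cancer therapy. That is a deliberate choice, and the gap does not affect it.
- *That treatment beyond progression feeds the problem into ORR.* Data after progression do not enter ORR.
- *That patients on savolitinib alone are part of the conflict.* Table J3 deals with co-administration with osimertinib and permits nothing with savolitinib alone.
- *That AEs on concurrent chemotherapy should be handled like those after discontinuation.* Under 9.4.3 that would take events in patients still on study drug out of the safety summaries. Keeping them in is the cautious course. Causality is assessed for every AE, and for SAEs also against other medication.

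**Conclusion.** The contradiction between Table J3 and Sections 4.1.1 and 4.1.2 is real, stands in the current version, and needs to be reconciled. Its statistical consequence is narrow: a response before progression, on a non-study anti-cancer drug given alongside study treatment, would be credited to the randomised arm. Each such patient weighs 3.6 points of that arm's ORR at 28 per arm, and 5 to 10 points if 20 to 10 per arm were reached. Those smaller sizes are assumed. The number of patients is unknown and probably very small or zero, so this is a cheap safeguard and not evidence that the result will be biased. The conclusion rests on the protocol text alone; an SAP that already handles concurrent therapy would close the ORR part. No view is taken on which of the two clinical statements is right.

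**What to change.** 1. **Reconcile** Table J3 with Sections 4.1.1 and 4.1.2 so that one rule on other anti-cancer agents with osimertinib applies, with a cross-reference between them. Which rule that is remains a clinical decision for the sponsor.
2. **Section 9.4.2.1:** do not count a CR or PR first documented after the start of any non-study systemic anti-cancer therapy, whether or not study treatment was discontinued. The patient stays in the denominator as a non-responder. The word systemic keeps the present treatment of radiotherapy. This works whichever clinical rule is kept.
3. **Section 9.4.3:** keep events that occur on study drug in the summaries. At most, flag in the listings those that start after concurrent anti-cancer therapy.

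The cost is an edit to the table or the design text and a sentence or two in the analysis sections, made before unblinding. Start dates are already collected, so no new data are needed. The downside is that a patient whose response was in truth due to study treatment could lose responder status because a cytotoxic had been added first.

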### **J 4 Medicines whose Exposures may be Affected by Savolitinib that AstraZeneca Strongly Recommend are not Combined with Savolitinib**

Cytochrome P450 3A4 substrates which have a narrow therapeutic range must not be taken within 2 weeks of the first dose of savolitinib treatment (3 weeks for St John's Wort) and for 3 weeks after the last dose of savolitinib.

Patients are not permitted to receive warfarin when patients are treated with savolitinib. Low molecular weight heparin is allowed.

Any cytotoxic chemotherapy, investigational agents or other anti-cancer drugs for the treatment of advanced NSCLC from a previous treatment regimen or clinical study within 14 days of the first dose of savolitinib.

